**Table 1 Time line**

ACTIVITIES	Month
Finalization of MOU, protocol, budget, and contract	1-2
Approval survey protocol	2-3
Sample design; selection PSUs	4
Recruitment	3-4
Household listing manual, adaptation, and training	5
Sample update, household listing (fieldwork)	5-7
Finalization Questionnaire content	3
Preparation Manuals	4
Translation questionnaires/manuals	4-6
Sensitization for data collection	6-11
Pretest (training and fieldwork)	6-7
Questionnaire/manuals review/printing	7-8
Training main survey	8-9
Fieldwork for data collection	9-14
Data processing (entry and editing)	10-15
Preliminary results	15-16
Analysis, report writing	16-19
Finalization of final report at ICF International	19
Printing of final report and key finding	20-22
National seminar	23

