#### 8. Access to HIV counseling and testing and receipt of HIV test results by survey Participants

The Rwandan MOH and RDHS V, 2014-15 stakeholders believe there is an ethical obligation to maximize access to HIV testing and receipt of HIV test results among RDHS 2014-15 survey participants. At the same time, it is imperative that current HIV testing service delivery, which remains primarily facility-based, not be disrupted and that limited resources have the greatest impact.

Currently, Rwanda MOH does not allow HIV rapid testing to be conducted by non-laboratory technicians. Countrywide, facility-based services have been scaled up tremendously in Rwanda; currently, roughly 485 health facilities in the country offer HIV counseling and testing (HCT) services from which 430 give the ART package. By June of 2012, 2,908,146 HIV tests were administered in a population of about 10 million. This level of HCT scale-up will help to ensure that survey participants are not required to travel more than 5-10 km to health facilities. Since HCT will be conducted in facilities, all participants who consent for HIV Testing during the survey will be advised to go to the nearest HCT and all HIV positive individuals will receive care and treatment according to national protocol and guidelines. Community health workers will be involved in community sensitizations in order to increase health services seeking for appropriate HIV management follow-up for HIV positive study participants.

For the above reasons, the RDHS-V, 2014-15 Steering and Technical Committees propose the following “enhanced” voucher-based approach:

1. All pre-survey implementation community sensitization activities will emphasize the importance of receiving HIV counseling and testing (HCT).
2. At the end of the survey interview, all survey participants, eligible for testing, regardless of whether or not they provided blood for HIV testing in the survey, will be encouraged to seek HCT and given a voucher which includes participant barcode by survey staff, and an

informational brochure which includes the following:

- Information about all existing facility-based VCT services within a 10 km radius.
  - A value of up to 2,500 FRW (~\$3.85) for transportation, to be reimbursed by local health facilities to the survey participant.
  - A value of 2,000 FRW (~\$3.07) for food and beverages in compensation for their time, to be reimbursed by local health facilities to the survey participant.

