3. Community health workers (CHW) in each sector (average 3-4) will be informed of the survey Enumeration Areas (EAs) selected in their sectors. They will follow-up by implementing community-based sensitization and mobilization campaigns within these EAs in order to encourage all inhabitants to seek HCT. This activity is not considered a part of routine CHW activities and thus is requiring of compensation. For the additional work burden associated with supporting this HCT promotion activity, a value of 500 FRW (\$0.77, based on 650 FRW = 1 USD) will be allocated to CHWs for each survey participant referred for and receiving HCT, including results. This is the current level of compensation provided to facility-based health workers for provision of HCT to one person under the Performance Based Financing (PBF) program and is more than the amount of compensation provided to CHWs for referrals under the community PBF program. Example, if a CHW successfully refers 10 survey participants for HCT services = 5,000 FRW in reimbursement by the local health facility.
  4. Local health facility staff will also be given a list of EAs from their sector, and will be encouraged to mobilize the respective CHWs to carry out community mobilization efforts to promote HCT using the national HIV rapid testing algorithm. This activity is not considered a part of routine health service delivery and will likely result in an increased work burden. For the additional work burden associated with supporting this ancillary HCT activity a value of 500 FRW (\$0.77) will be allocated to each health worker for each survey participant that they provide with HCT at the health facility, including results. Example, if a health care worker successfully provides 10 survey participants with HCT services = 5,000 FRW in reimbursement by the local health facility.

This approach would result in an estimated expenditure of ~US\$10/survey participant who receives HCT, if all the steps are followed. This approach was relatively successful in the RDHS 2010, with the high uptake of HCT among survey participants.

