**Table A.8 Prior HIV testing by current HIV status**

Percent distribution of women and men age 15-49 who tested HIV positive and who tested HIV negative by HIV testing status prior to the survey, Rwanda 2014-15

	Women	Men	Total
--	-------	-----	-------

HIV testing prior to the survey	HIV positive	HIV negative	HIV positive	HIV negative	HIV positive	HIV negativ
Previously tested						
Disclosed positive result						
Disclosed negative result						
Declined to disclose result						
Did not receive result of last test						
Not previously tested						
Total	100.0	100.0	100.0	100.0	100.0	100.0
Number						

Table A.9 HIV prevalence by male circumcision

Among men age 15-49 who were tested for HIV, the percentage HIV positive by whether circumcised, according to background characteristics, Rwanda 2014-15

Background characteristic	Circumcised		Uncircumcised	
	Percentage HIV positive	Number of men	Percentage HIV positive	Number of men
Age				
15-19				
20-24				
25-29				
30-34				
35-39				
40-44				
45-49				
Religion				
-				
-				
-				
-				
Urban				
Rural				
Province				
Kigali				
South				
West				
North				
East				
Education				
None				
Primary				
Secondary				
More than				
Wealth quintile				
Lowest				
Second				
Middle				
Fourth				
Highest				
Total 15-49				
50-59				
Total 15-59				

Table A.10 HIV prevalence among couples

Percent distribution of couples living in the same household, both of whom were tested for HIV, by the HIV status, according to background characteristics, Rwanda 2014-15

Background characteristic	Both HIV	Man HIV positive,	Woman HIV positive,	Both HIV	Total	Number
Woman's age						
15-19					100.0	
20-29					100.0	
30-39					100.0	
40-49					100.0	
Man's age						
15-19					100.0	
20-29					100.0	
30-39					100.0	
40-49					100.0	
50-54					100.0	
Age difference between partners						
Woman older					100.0	
Same age/man older					100.0	
Man older by 5-9					100.0	
Man older by 10-14					100.0	
Man older by 15+					100.0	
Type of union						
Monogamous					100.0	
Polygynous					100.0	
Residence						
Urban					100.0	
Rural					100.0	
Province						
Kigali					100.0	
South					100.0	
West					100.0	
North					100.0	
East					100.0	
Woman's education						
None					100.0	
Primary					100.0	
Secondary					100.0	
More than secondary					100.0	
Man's education						
None					100.0	
Primary					100.0	
Secondary					100.0	

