	Risk of MTCT can be reduce by taking ARVs (2)	≥15%	2010 RDHS
	Both (1) and (2)	≥15%	2010 RDHS
g. Knowledge of PMTCT: women	HIV can be transmitted by breastfeeding (1)	>30%	2010 RDHS
	Risk of MTCT can be reduce by taking ARVs (2)	>30%	2010 RDHS
	Both (1) and (2)	>30%	2010 RDHS
h. Accepting attitude: women	Willing to care for family member with AIDS	≥15%	2010 RDHS
	Buying fresh vegetable from vendor with AIDS	≥15%	2010 RDHS
	Agreeing that female teacher with AIDS and not sick	≥15%	2010 RDHS
	Would not keep a secret of family member with AIDS	≥15%	2010 RDHS
i. Accepting attitude: men	Willing to care for family member with AIDS	>30%	2010 RDHS
	Buying fresh vegetable from vendor with AIDS	≥30%	2010 RDHS
	Agreeing that female teacher with AIDS and not sick	≥30%	2010 RDHS
	Would not keep a secret of family member with AIDS	>30%	2010 RDHS
j. Negotiating safer sex with a husband if he has STD: women	Refusing sex (1)	≥15%	2010 RDHS
	Asking to use condom (2)	≥15%	2010 RDHS
	Both (1) and (2)	≥15%	2010 RDHS
k. Support of education about condom use in children: women	(Yes/no)	≥15%	2010 RDHS

l. Support of education about condom use in children: men 18-		≥30%	2010 RDHS
m. Ever tested for HIV: women	(yes/no)	>15%	2010 RDHS
n. Ever tested for HIV: men	(yes/no)	≥30%	2010 RDHS
o. Received counseling during	(yes/no)	≥35%	2010 RDHS
p. Knowledge about AIDS in youth	Knowledge of AIDS and a source of condom	≥25%	2010 RDHS
q. Never had sex among youth (15-	Knowledge of AIDS and a source of condom	≥45%	2010 RDHS
*Each category of indicators must be at least at this level or higher allowing for the computation at the district-level with relative standard error of 20%. These indicators were selected based on the 2010 RDHS. If the levels of indicators drop lower than the			

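### HIV-testing promotion starts before fieldwork and campaigns in sampled areas need not wait for the interviews, so ever-tested and prior-testing indicators may be inflated

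*Protocol*

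**What the plan says.** Section 8 of the HIV testing part (access to HCT and receipt of results) sets out four steps.

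- Step 1 concerns the period before the survey: "All pre-survey implementation community sensitization activities will emphasize the importance of receiving HIV counseling and testing (HCT"). No place is named.
- Step 2 gives each eligible participant a voucher when the interview ends.
- Step 3 concerns CHWs, who "will be informed of the survey Enumeration Areas (EAs) selected in their sectors". It continues: "They will follow-up by implementing community-based sensitization and mobilization campaigns within these EAs in order to encourage all inhabitants to seek HCT". It adds: "This activity is not considered a part of routine CHW activities and thus is requiring of compensation". They earn 500 FRW per survey participant referred for and receiving HCT. No date is given.
- Step 4 gives facility staff the EA list too, and asks them to encourage the CHWs' mobilization.

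Table 1 places "Sensitization for data collection" in months 6-11 and "Fieldwork for data collection" in months 9-14. Primary sampling units are selected in month 4.

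Section 9 (tracking, monitoring, and evaluation) speaks of an HCT promotion period during and after the survey. It asks CHWs to record the EA, date, location and number of persons reached for each campaign. No analytic use of the date is stated.

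The indicators at issue are "m. Ever tested for HIV: women" and its counterpart for men (Appendix B), HIV prevalence by prior testing (Table A.7), and the distribution of HIV-positive and HIV-negative respondents "by HIV testing status prior to the survey" (Table A.8). Section 9 also plans to estimate the share who did not know their serostatus, to inform the return of results in future surveys.

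**The concern.** The promoted behaviour and the measured behaviour are the same: having an HIV test. Anyone who tests because of the promotion and is interviewed afterwards is counted as previously tested.

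There are two routes. Pre-survey messages must stress HCT, and sensitization starts three months before fieldwork (month 6 against month 9). The EA list exists from month 4, and nothing stops a CHW campaign from running in a sampled EA before the team arrives or while it is still interviewing. The second route matters more for representativeness: the campaigns are beyond routine CHW work and confined to sampled EAs, so an early one would make the sample differ from the areas it stands for.

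The weights described under selection probability and sampling weight adjust for unequal selection and non-response. They cannot adjust for behaviour changed by being in the sample.

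A further exposure is possible in the two oversampled areas, whose extra households are visited after the main survey. If they share EAs with the main sample, campaigns may already have run there.

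**Working it through.** **Inputs from the Protocol.** National n = 13,470 women, district n = 440 women and Deft = 1.5, all from the expected survey precision tables. The national n agrees with the allocation: 27 × 438 + 3 × 548 = 13,470.

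**Inputs not in the Protocol (assumed).** Share never tested: 10-40%. Share of those who test because of promotion before their own interview: 2-20%, averaged over all clusters, including any that had no early promotion.

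**Step 1: reproduce the plan's precision.** SE = Deft × √(P(1−P)/n), with limits P ± 2 SE.
- National, P = 0.10: 1.5 × √(0.09/13,470) = 0.0039, limits 0.092-0.108. The table prints 0.004 and the same limits. The other national rows agree as well.
- District, P = 0.10: 1.5 × √(0.09/440) = 0.0215, limits 0.057-0.143. The printed limits agree. The printed SE of 0.022 is what n = 438 gives after rounding, which is immaterial here. The other district rows agree.

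**Step 2: shift compared with sampling error.** Shift b = (share never tested) × (share of them prompted before interview). Half-width = 1.96 × SE, at P = 1 − share never tested. Coverage of a nominal 95% interval = Φ(1.96 − b/SE) − Φ(−1.96 − b/SE).

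Worked case, 20% never tested and 5% prompted: b = 0.20 × 0.05 = 1.0 point. National SE = 1.5 × √(0.16/13,470) = 0.52 points and half-width = 1.01 points. Coverage is about 51%.

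| Never tested | Prompted | Shift (points) | National half-width | National coverage | District half-width | District coverage |
|---|---|---|---|---|---|---|
| 10% | 2% | 0.2 | 0.76 | 92% | 4.2 | 95% |
| 20% | 5% | 1.0 | 1.01 | 51% | 5.6 | 94% |
| 30% | 10% | 3.0 | 1.16 | 0.1% | 6.4 | 85% |
| 40% | 20% | 8.0 | 1.24 | about 0 | 6.9 | 37% |

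**Step 3: HIV-positive respondents in Table A.8.** Expected number: 0.030 × 12,207 ≈ 366 (HIV precision table). With an assumed P = 0.75 and Deft = 1.5, SE = 1.5 × √(0.1875/366) ≈ 3.4 points. A shift of 1 point is about 0.3 SE in that column, so the national comparison in Step 2 does not carry over to it.

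**The case against.** A reader might infer that the plan delivers HIV-testing promotion in the sampled EAs before the interviews. The documents do not say so. Step 1 is dated but names no place, and the Protocol elsewhere describes public awareness work through the media and local government structures. If those messages are nationwide, sampled EAs do not differ from the rest of the country by that route, even if the level moves everywhere. Step 3 names the place but gives no date. Its follow-up wording, its position after the end-of-interview voucher and a payment tied to survey participants all suggest work after the interview. Vouchers and payments cannot alter answers already given.

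The size is also open to challenge. Background testing is heavy (section 8 reports 2,908,146 tests in a population of about 10 million by June 2012), and people who would have tested anyway are not bias. Only testing caused by promotion counts, so the low end of the range lies inside national sampling error.

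These points stand, and they limit the claim. They do not supply the missing rule. Following up can equally mean acting on the EA list just received, and section 9 places promotion during the survey as well as after it. HCT promotion is a deliberate choice under a stated ethical obligation, but changing its order does not withdraw it.

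**Conclusion.** The concern holds as a sequencing gap. The plan promotes HCT before fieldwork, gives out the sampled-EA list for non-routine HCT campaigns, and sets no order between those campaigns and the cluster's interviews. The ever-tested and prior-testing indicators may therefore be inflated. That they will be inflated is not shown.

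The size cannot be computed from the documents. The range of 0.2 to 8 points rests wholly on the two assumed shares. Within it, a shift of about 1 point already matches the national 95% half-width for women, whereas district estimates are little affected until the shift reaches several points. A bias of many standard errors across all these indicators is not supported.

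A reader might extend the point to HIV-knowledge indicators. The documents do not support this: step 1 promotes testing, not knowledge of transmission or prevention, and the HIV brochures have no stated timing before the interview. The point is worth settling before fieldwork because the correction is cheap.

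**What to change.** State the order in section 8 and Table 1:

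1. Pre-survey sensitization covers taking part in the survey. HCT messages are held back.
2. The EA list goes to CHWs and facilities, and HCT mobilization starts in an EA, only after that cluster's interviews and blood collection are complete. This includes any oversampled households in the same EA.
3. Vouchers at the end of the interview stay as planned.
4. The campaign dates that CHWs already record are compared with each cluster's interview dates to identify exposure before interview. The result is reported as a limitation of the ever-tested and prior-testing indicators.

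This needs no additional sample and no new staff. Mobilization starts later in each EA, and releasing the list cluster by cluster needs some coordination. Section 8 says this approach was used in RDHS 2010, so the new order may differ from that survey's, which should be noted beside any trend comparison.

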#### *9. Tracking, monitoring, and evaluation.*

Rigorous monitoring and evaluation will accompany this enhanced voucher distribution plan which aims primarily to promote survey participants' access to HCT and receipt of HIV test results. During the survey and post-survey HCT promotion period, health facility HCT staff will be encouraged to ask all persons seeking HCT whether they have a survey voucher, if not presented to them. In addition, as above a bar code will be attached to the voucher. This bar code will be used to link the survey information with the voucher- and HCT service data; however the information will remain strictly anonymous. CHWs will be asked to record the EAs where they carried out community sensitization campaigns, along with other corroboratory information, such as date, location, number of persons reached. CHWs will be compensated based on persons who are confirmed to have received HCT services, including HIV test results, at the local health center(s) corresponding to the EAs.

HCT staff will be asked to document the following information in dedicated RDHS-V's HCT log books: current date and rapid HIV test results. In addition, the number of the participant recorded in the HCT log will be written on the bar code sticker, and will be used to anonymously link the survey, voucher and log information. The information recorded on the voucher will also be used to determine compensation of facility-based HCT staff according to the above guidelines. Routine HCT client data will also be recorded in standard national HCT registers, however only standard data elements will be included, i.e. there will be no recording of bar codes or other survey-related information. During implementation of the survey and for 3 months afterwards, RBC's HIV/AIDS division, MOH, and District Hospital staff will be required to support this activity through routine supervision. After the 3-month post-survey follow-up period all vouchers and log books will be collected and data will be entered into an EPI-Info database at RBC's HIV division for analysis. After linkage of the databases the vouchers and logs will be destroyed. Of note, laboratory testing of the blood samples collected during the survey will not be delayed by the HCT promotion activity; linkage of the databases can be performed after the fact using the anonymous bar codes.

ICF International will release a clean version of the main database to RBC's HIV division for linkage (using the bar codes) to the HCT dataset within 6 months of completion of data collection RBC's HIV/AIDS division and MOH will analyze the data to address the question of what percent of persons did not know their serostatus and those data will be used to inform returning test results in future surveys.

### **Anemia testing**

Anemia testing will be part of the RDHS-V, 2014-15. RBC/NRL Division will lead activities of training, collection of anemia. The Malaria & OPDD will be responsible of the analysis of anemia.

Blood specimens for anemia testing will be collected from all children aged 6-59 months, if the parent or guardian consents to the test. Blood specimens will also be collected from all eligible women who voluntarily consent to the testing. Anemia testing will be carried out in the households selected for the man's survey.

For the anemia testing, a blood drop will be obtained from each eligible woman and child by picking the finger (or heel in the case of very young children). The blood drop will be tested using the HemoCue system (photometer and microcuvette), which assesses the level of hemoglobin in the blood. Results will be provided immediately following the anemia testing both verbally and in writing for each of the individuals who are tested. All survey participants eligible for anemia testing will receive a brochure explaining what is anemia, and providing advice regarding types of food to eat to avoid iron deficiency. Results of the anemia test will be recorded in the DHS questionnaire.

Individuals whose hemoglobin levels fall below designated cutoff points (9 g/dl for pregnant women and 7 g/dl for women who are not pregnant (or do not know if they are pregnant), and children under age five) and who are severely anemic will be referred for assessment and treatment to a health facility.

### **Training for all study personnel**

Seventeen (17) teams of field staff will be recruited by NISR for the needs of the main survey. Each team will be composed of a team leader (male), one controller or field editor (female), three female interviewers, one male interviewer, and a lab technician in charge of blood drawings and anthropometric measurements. However all interviewers will receive special training for the tests.

All candidates for the field staff positions will be selected on the basis of their maturity, their skill in communicating, their level of education, their knowledge of the national language and availability to work far from home for a period of at 5.1 months. Everything will be done to involve qualified field personnel whose qualifications will be established beforehand by the technical team for the survey.

The candidates will take classroom training for about four weeks, dealing with all aspects of the survey. A greater number of candidates than needed will be trained so that the best of these may be chosen and, so that changes may eventually be made, as needed, during the first days in the field. The training will take place in a venue of sufficient size to accommodate the candidates and where it will be possible to take meals. NISR will provide trainers and ICF International will assist them. Presentations on specific topics will be made by personnel from the Ministry of Health or other appropriate institutions.

The training program will include: a detailed description of the content of the questionnaires; a presentation of interview techniques; explanations on how to fill out the questionnaires; and training on the taking of anthropometric measurements. The training will include presentations, practice interviews in the classroom, and practice interviews in the field. Each interviewer will carry out at least five interviews throughout the training period.

A special training session of about one week will be organized for persons who will be in charge of the malaria, anemia and HIV tests. The training will focus on: the procedures to be used in obtaining voluntary consent from respondents; the techniques to be used for taking blood samples; to use rapid test and blood smear for malaria, the procedure to treat the patient with RDT malaria positive, for referring participants who need follow-up for malaria or malnutrition and providing the HCT vouchers to eligible participants; the procedures for handling and storing the samples on filter paper until their transport to the laboratory; and the procedures for eliminating bio-hazardous products. The training will include a detailed presentation on the procedure to follow for the transfer of samples from the field to the laboratory. All personnel in the central office of the RDHS-V and those from the NRL who will be involved in the activities of the HIV test, as well as field personnel, will participate in this aspect of the training. Personnel from the NRL will be trained on the manner to record test results and the way to deliver results to NISR when all the survey activities are completed.

A half day of training will be devoted to giving information to all personnel of the RDHS-V (whether they are involved or not in the HIV test) about the AIDS epidemic and the means of prevention as well as on the reasons why the HIV test is included in the survey. Questions on stigmatization, misconceptions, and questions of confidentiality will be dealt with during this training.

Finally, at least one day will be reserved for team leaders and female supervisors to train them in the manner of observing interviews in the field, editing completed questionnaires and controlling the quality of samples.

After having completed the training session, every field staff member must have an in depth knowledge of their role to play in the collection of data in order to achieve maximum effectiveness in the fieldwork.

